5. OUTCOME MEASURES

5.1 Primary Outcome Measure

The primary outcome measure is diagnostic accuracy of the multiplex PCR test, expressed as sensitivity, specificity, and positive and negative predictive values, with uncertainty expressed using 95% confidence limits.

In the primary analysis, these will be calculated by using the paired blood culture as the reference standard (i.e. the blood culture that had been taken contemporaneously). True positivity will be defined as the PCR test detecting the same genus of organism as identified in the paired blood culture.

Acknowledging that there is no perfect reference standard for sepsis, a secondary analysis will be undertaken, using a less stringent reference standard to resolve discrepant results in a 'fair umpire' test³⁷. This will be applied when the PCR test is positive and the paired blood culture is negative. In this analysis, true positivity will be defined as either:

- (i) culture of the same genus of organism in blood or other sterile site culture within 7 days of the test sample being taken; or
- (ii) culture of the same genus of organism from a non-sterile anatomic site within 3 days of the test sample being taken which is judged, by the patient's clinical team, to represent a focus of infection.

Furthermore we will undertake analysis of the primary outcome measure when multiplex PCR testing is conducted at the point of care, vs. centrally, using both the paired blood culture and the fair umpire test. The primary outcome (diagnostic accuracy) will be re-analysed including only those samples tested at the point of care and compared to the same metrics obtained when only those samples tested centrally are included.

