9. SCHEDULE OF ASSESSMENTS AND STUDY PROCEDURES

9.1 Schedule of Assessments

All patients will be evaluated during the study and data collected at each of the following time-points. For routinely collected clinical data the NHS record will be the source document and for study specific clinical measurements the CRF will be the source document.

Baseline

- Patient Demographics (date of birth, gender)
- Date and Time of ICU admission
- Suspected Source of Sepsis
- The Acute Physiology and Chronic Health Evaluation score (APACHE II) at ICU admission

At Sampling

- Site, Date and Time of sampling
- Previous Antibiotic regimens within 3 calendar days of sampling (Yes/No)
- Determinants of SOFA Score at time of sampling

Additional Assessments

- Paired blood culture result
- Multiplex PCR result
- Date and Time Multiplex PCR test completed
- Date and Time clinical team informed of blood culture result
- Results of additional blood and other sterile anatomic site cultures taken within +/-7 days of the research blood sample for suspected sepsis will also be recorded.
- Results of cultures from non-sterile anatomic sites within +/-3 days of the research blood sample for suspected sepsis will be recorded. Whether the treating physician judged this to represent a clinically-suspected focus of infection will also be recorded.

At Discharge

- Date of critical care discharge
- Date of hospital discharge

Mortality

- Date of death (within 28 days of recruitment)

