11. STATISTICAL CONSIDERATIONS

11.1 Sample Size

The sample size is based on:

- (i) an assumed 10% event rate for true positive results among specimens collected – this is based on pilot data collected in a single centre.
- (ii) an estimated overall test sensitivity of 90%, and specificity of 95%.
- (iii) the need to ensure that the overall test sensitivity is estimated with a high degree of precision. We have set this precision as +/-3%, at the 95% confidence level.
- (iv) the ability to assess performance of the test for detecting pathogens for which true positive results are expected as infrequently as 1 in 500 tests. We have set the precision for this as +/-20%, at the 95% confidence level
- (v) Given a 10% event rate for true positive results, a sample size that achieves the proposed degrees of precision for the sensitivity estimate will enable the specificity of the test to be measured with even greater precision.

With an assumed sensitivity of 90% with a 10% true positivity rate, in order to estimate the overall sensitivity of the test with a precision of +/-3% at the 95% confidence level, 3851 samples are required. For uncommon pathogens, with an assumed sensitivity of 90% with a 0.2% true positivity rate, in order to estimate the overall sensitivity of the test with a precision of +/-20% at the 95% confidence level, 4501 samples are required. Therefore, 4501 samples will be tested to assess the diagnostic accuracy of the test using these parameters.

The sample has not been inflated for dropouts or missing data because: (i) research sampling is not necessary after the day of enrolment; (ii) the follow-up period is very short; and (iii) the nature of ICU care presents minimal risk of attrition for follow-up.

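### The secondary 'fair umpire' analysis re-examines only PCR-positive, culture-negative samples, so its sensitivity cannot fall and its NPV cannot move, whatever the extra cultures show

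*Protocol*

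**What the plan says.** Protocol 5.1 makes the paired blood culture the primary reference standard: "True positivity will be defined as the PCR test detecting the same genus of organism as identified in the paired blood culture". Because no reference standard for sepsis is perfect, it adds a secondary analysis "using a less stringent reference standard to resolve discrepant results in a 'fair umpire' test". The scope of that analysis is fixed in one sentence: "This will be applied when the PCR test is positive and the paired blood culture is negative". Two routes then make such a sample a true positive:

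- "culture of the same genus of organism in blood or other sterile site culture within 7 days of the test sample being taken";
- "culture of the same genus of organism from a non-sterile anatomic site within 3 days of the test sample being taken", provided the clinical team judges that site to be a focus of infection.

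No rule in 5.1 re-examines a sample on which PCR and paired culture were both negative. The same section reuses the fair umpire, alongside the paired culture, when accuracy at the point of care is compared with accuracy of central testing.

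The data collection is wider than the rule. Section 9.1 lists, with no restriction by PCR result, "Results of additional blood and other sterile anatomic site cultures taken within +/-7 days of the research blood sample" and "Results of cultures from non-sterile anatomic sites within +/-3 days of the research blood sample for suspected sepsis will be recorded", together with the treating physician's judgement on whether a non-sterile culture represented a focus.

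**The concern.** Whether the extra cultures count depends on the result of the test being evaluated. If PCR was positive, a later or neighbouring culture can turn an apparent error into a success. If PCR was negative, the same kind of culture is ignored and the sample stays a true negative. This is the bias of discrepant analysis.

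The analysis is the protocol's stated answer to the imperfection of blood culture. As written, that answer can only favour the test on sensitivity and cannot count against it on NPV. It also feeds the point-of-care versus central comparison. There, the setting with more PCR-positive, culture-negative results is offered more samples to convert, and so more scope for its sensitivity to rise.

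**Working it through.** **Inputs.** Protocol 11.1 gives 4501 samples, sensitivity 90%, specificity 95% and "an assumed 10% event rate for true positive results among specimens collected". I read that rate as the proportion of samples positive on the reference standard, because this reading reproduces the sample size.

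**The plan's own figures.** Reference-positives needed = 1.96² × 0.9 × 0.1 / d².
- d = 0.03: 384.1, rounded up to 385; 385 / 0.10 = 3850 (stated 3851).
- d = 0.20: 8.64, rounded up to 9; 9 / 0.002 = 4500 (stated 4501).

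Both agree to within one sample and are not in dispute.

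**Expected primary table.** Reference-positive: 450.1, of which TP 405.1 and FN 45.0. Reference-negative: 4050.9, of which FP 202.5 and TN 3848.4.

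**Effect of the rule.** If k false positives are confirmed:
- sensitivity = (TP + k) / (TP + k + FN), which cannot fall;
- specificity = TN / (TN + FP − k), which cannot fall;
- PPV = (TP + k) / (TP + FP), which cannot fall;
- NPV = TN / (TN + FN), which does not contain k.

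**Effect of applying the standard to everyone.** If j double-negatives also have a qualifying culture, they move from TN to FN:
- sensitivity = (TP + k) / (TP + k + FN + j);
- specificity = (TN − j) / (TN − j + FP − k);
- PPV is unchanged from the one-sided rule;
- NPV = (TN − j) / (TN + FN).

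The protocol gives no confirmation rates. I assume 25% of false positives are confirmed (k = 50.6) and vary the share q of double-negatives that qualify (j = 3848.4q). I also assume no PCR-positive sample has only a different genus in its cultures.

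| Analysis | Sensitivity | Specificity | PPV | NPV |
|---|---|---|---|---|
| Primary (paired culture) | 90.0% | 95.0% | 66.7% | 98.8% |
| Fair umpire as written | 91.0% | 96.2% | 75.0% | 98.8% |
| All samples, q = 1% | 84.5% | 96.2% | 75.0% | 97.9% |
| All samples, q = 2% | 78.9% | 96.1% | 75.0% | 96.9% |
| All samples, q = 5% | 65.8% | 96.0% | 75.0% | 93.9% |

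For example, the rule as written gives (405.1 + 50.6) / (450.1 + 50.6) = 455.7 / 500.7 = 91.0%. At q = 2%, j = 77.0 and sensitivity is 455.7 / 577.7 = 78.9%.

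**Threshold.** Sensitivity falls below 90% when FN + j > (TP + k) / 9. Since TP / 9 = FN here, that is j > k / 9 = 5.6, so about 6 of 3848 double-negatives (0.15%). With 10% of false positives confirmed the threshold is 2.3 samples (0.06%); with 50% it is 11.3 (0.29%).

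**A test unrelated to infection.** Suppose PCR is positive at random in 5% of samples and 25% of all culture-negatives would meet the umpire criteria, ignoring genus. Then TP = 22.5, FN = 427.6, FP = 202.5 and k = 50.6. The rule lifts sensitivity from 5.0% to (22.5 + 50.6) / 500.7 = 14.6%. Applied to every culture-negative sample (j = 0.25 × 3848.4 = 962.1), the same standard returns 73.1 / 1462.8 = 5.0%. The gain comes only from choosing which samples to re-examine. The same-genus requirement would shrink it, so this shows direction, not size.

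**The case against.** The strongest reply has five parts.

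- *The analysis is secondary.* This stands. The primary analysis uses the paired culture for every sample, 11.2 bases the accuracy assessment on conventional culture, and the sample size does not depend on the umpire. The protocol also openly calls the standard less stringent.
- *Not every improvement is an artefact.* This stands. A reader might infer that the rises in PPV and specificity are produced by the one-sidedness. They are not, in the main. PPV uses only PCR-positive samples and is 75.0% under either rule. Of the 1.2-point rise in specificity, at least 1.0 point survives at q up to 5%; it vanishes only if double-negatives qualify as often as PCR-positives do.
- *The reported gain is small.* Sensitivity moves from 90.0% to 91.0%, inside the ±3% precision in 11.1. That is true against the primary analysis. The more telling gap is between 91.0% and the value under an even-handed use of the same standard, which is 6.5 points at q = 1%.
- *Clinical teams are blinded to PCR (6.1).* Blinding protects the judgement of focus, so the documents do not support reading that judgement as driven by PCR. It does not alter which samples are re-examined.
- *A standard applied to everyone may be unfair to PCR.* A culture up to 7 days away, or from a non-sterile site, may reflect a separate focus or a later episode; 7.4 itself allows re-sampling after 5 days. This is a fair caution. But the rule already accepts those cultures as evidence when they help the test, and it cannot reasonably accept them in one direction only.

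**Conclusion.** The point holds, as a should-fix for a secondary analysis. That sensitivity cannot fall and NPV cannot move is an algebraic certainty and needs no assumption. The size is not certain: it depends on confirmation rates that the protocol does not give. At the protocol's own accuracy assumptions and an assumed 25% confirmation of false positives, about 6 qualifying double-negatives out of 3848 are enough to take sensitivity below 90%, while the rule reports 91.0% regardless.

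Two stronger readings should be avoided. First, a reader might take 79% or 66% as a forecast of the test's sensitivity; these figures only show what follows from assumed rates of 2% and 5%. Second, a reader might conclude that the NPV has no reference standard at all. It has one: it equals the primary NPV against paired culture. It simply says nothing about the extended standard under which it would be reported.

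**What to change.** In 5.1, define the extended reference standard without reference to the PCR result and apply it to every sample:

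- A sample is reference-positive if the paired culture is positive, or a blood or other sterile-site culture is positive within 7 days, or a non-sterile culture judged to be a focus of infection is positive within 3 days.
- It is a true positive only if PCR detects the same genus as a qualifying culture.
- State in advance how a PCR-positive sample is classified when its cultures grew only a different genus.
- Use this definition for the point-of-care versus central comparison as well.

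Keep the one-sided resolution only as a descriptive figure: the proportion of PCR-positive, culture-negative results later corroborated. Do not derive sensitivity, specificity or NPV from it.

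The cost is mainly redrafting 5.1, including the genus rule. The cultures and the focus judgement are already collected under 9.1, so no new data are needed. The change should be made before PCR results are compared with the cultures. The downside is that sensitivity and NPV under the extended standard will look less favourable. The report should say that some qualifying cultures may reflect a separate focus or a later episode.

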9.2.2.1 Sample for Multiplex PCR Testing

Approximately the first half of the study samples will be initially stored at site and transferred in batches to a central laboratory in Queen's University Belfast, for testing using the Multiplex PCR device, in accordance with the Sample Processing Guideline. Subsequent samples will be analysed using the Multiplex PCR device at the POC by ICU clinical and/or research and/or technical staff at participating sites who have received training in the use of the Multiplex PCR testing device and transferred in batches to a central laboratory in Queen's University Belfast for testing using the Multiplex PCR device.

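### The bedside-versus-central comparison is defined by two sets of samples that either overlap or divide by study period, although later samples are tested both ways and could be compared in pairs

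*Protocol*

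**What the plan says.** Protocol section 5.1 plans a comparison of accuracy by place of testing, against both the paired culture and the fair-umpire reference. The primary outcome is to be "re-analysed including only those samples tested at the point of care and compared to the same metrics obtained when only those samples tested centrally". The Study Summary lists this as secondary outcome (ii), although section 5.2 does not repeat it.

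Section 9.2.2.1 sets out which samples are tested where:

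- Early samples: "Approximately the first half of the study samples will be initially stored at site and transferred in batches to a central laboratory".
- Later samples: "Subsequent samples will be analysed using the Multiplex PCR device at the POC by ICU clinical and/or research and/or technical staff". The same sentence continues, after describing the staff as trained, "in the use of the Multiplex PCR testing device and transferred in batches to a central laboratory", again for testing on the device.

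Read literally, all samples are tested centrally and the POC samples are a subset of them, made up of the later part of recruitment.

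Section 11.1 gives the planning values: 4501 samples, "an assumed 10% event rate for true positive results among specimens collected", sensitivity of 90% and specificity of 95%. It does not size the POC-versus-central comparison.

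**The concern.** Section 5.1 defines the comparison by two sets of samples, but section 9.2.2.1 does not produce two separate sets. Two readings of the central set are possible, and each causes a problem.

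- **All samples.** The restriction to centrally tested samples then excludes nothing, and every POC sample is in both sets. The first half contributes to the central figure only, so a change over time in case mix, sites, storage or device handling leaks into the difference.
- **First half only.** The sets are then disjoint, but place of testing coincides exactly with study period. A difference between POC and central cannot be separated from a difference between early and late recruitment.

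The protocol already generates a cleaner contrast: two results on the same later sample. The sentence in 5.1 does not use it. At stake is whether a POC-central difference, or its absence, can be interpreted.

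**Working it through.** **Inputs.** From section 11.1: 4501 samples, 10% positivity, sensitivity 90%, specificity 95%. From section 9.2.2.1: a split at about half. The rate at which POC and central results disagree on the same sample, *d*, is not in the protocol. It is assumed here at 2%, 5% and 10% of culture-positive samples; under complete independence it would be 2 × 0.90 × 0.10 = 18%.

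**The plan's own figures.** Positives needed = 1.96² × 0.9 × 0.1 / precision².

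- Overall: 0.3457 / 0.03² = 384.1, rounded up to 385; 385 / 0.10 = 3850 (stated 3851).
- Uncommon pathogens: 0.3457 / 0.20² = 8.64, rounded up to 9; 9 / 0.002 = 4500 (stated 4501).

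Both reproduce to within one sample. They also show that the 10% is used as the share of samples that are reference-positive.

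**Numbers per half.** 4501 / 2 × 0.10 ≈ 225 culture-positive and 4501 / 2 × 0.90 ≈ 2025 culture-negative.

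**95% half-widths for the sensitivity difference**, with v = 0.9 × 0.1 = 0.09 and equal true sensitivities:

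- First half central against second half POC: 1.96 × √(2 × 0.09 / 225) = ±5.5 points.
- All central against POC, wrongly treated as independent: 1.96 × √(0.09/225 + 0.09/450) = ±4.8 points.
- All central against POC, allowing for the overlap: the variance is v/225 + v/450 − ρv/225 with ρ = 1 − d/(2v), which simplifies to (v + d)/450.
- Paired within the second half: 1.96 × √(d/225).

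| Assumed discordance *d* | Overlapping sets, true | Paired, second half |
|---|---|---|
| 2% | ±3.1 | ±1.8 |
| 5% | ±3.5 | ±2.9 |
| 10% | ±4.0 | ±4.1 |

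The last two columns are equal when (v + d)/450 = d/225, that is at d = v = 9%. Above that, pairing gives no gain in precision over the overlapping sets. At 18% the paired half-width is ±5.5, the same as for disjoint halves.

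**Specificity**, on about 2025 second-half culture-negatives, paired: ±0.6 points at 2% and ±1.0 at 5% discordance, against ±1.3 for disjoint halves.

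**Period drift.** Let sensitivity be s₁ in the first half and s₂ in the second, with no effect of place.

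- Overlapping sets: s₂ − (s₁ + s₂)/2 = (s₂ − s₁)/2, so half the drift appears as a POC effect.
- Disjoint halves: s₂ − s₁, so all of it does.
- Paired: s₂ − s₂ = 0.

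An illustrative 5-point drift gives a bias of 2.5, 5 and 0 points respectively.

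**Is a period difference plausible?** In the section 6.4 timeline, reading the rows in order (the extracted table may be misaligned), open sites rise from 1 to 12 over the first nine entries, by which point 864 samples have accrued, and then exceed 15. So 864 / 2250 ≈ 38% of first-half samples, and none of the second half, would come before the full set of sites is open.

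All half-widths ignore the repeat samples per patient that section 7.4 allows.

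**The case against.** The strongest reply is that 5.1 names no test, interval or independence assumption, and that a SAP, not shown here, could specify a paired interval. This stands as far as the method goes: a reader might infer that the protocol has chosen an independent-groups analysis, and it has not. It does not rescue the definition of the sets. An analysis faithful to the sentence must either put POC samples on both sides or split by study half, and period enters both ways.

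Three stronger inferences should also be resisted.

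- *That the paired data are thrown away.* Only the first-half reading leaves the later central results unused. On the literal reading both results enter, and it is the pairing that the wording leaves unused.
- *That the planned estimate is always noisier than it need be.* The ±5.5 points belongs to the first-half reading. Against the overlapping reading, pairing is more precise only below about 9% to 10% discordance, and discordance is unknown.
- *That the first half comes mainly from early-opening sites.* The timeline passes 2250 only at its 14th of 21 accrual entries (2303), but that does not measure site imbalance. On the same reading, over 60% of the first half accrues with all sites open.

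It is also fair that bedside performance itself is answered directly by POC results against culture, at about 1.96 × √(0.09/225) = ±3.9 points for sensitivity, whatever is done with the central results.

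**Conclusion.** The point holds, limited to the POC-versus-central comparison. Sections 5.1 and 9.2.2.1 together give a contrast that takes in half or all of any period drift, and in the overlapping case an independent-groups interval would be too wide (±4.8 against a true ±3.1 to ±4.0 points). A paired contrast within second-half samples removes the period bias and gives a valid interval. Whether it is also tighter depends on the assumed discordance. The figures rest on the section 11.1 planning values, an even split, equal true sensitivities and no clustering by patient.

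A reader might extend this to the primary accuracy estimates or to the 4501 sample size. Neither is affected: the primary analysis compares PCR with culture, and the sample size rests on precision for overall and uncommon-pathogen sensitivity. Nor would pairing isolate location alone, because the central result follows batching and transfer.

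**What to change.** Reword the sentence in section 5.1 so that:

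- the POC-central comparison uses second-half samples with both a POC and a central result;
- paired differences with 95% confidence intervals are given for sensitivity and specificity (McNemar-type) and for positive and negative predictive values (a paired method for predictive values), so that all four metrics now promised are kept;
- this is done against both the paired culture and the fair-umpire reference. Because 5.1 applies the umpire only when PCR is positive and culture negative, the text should say how a sample's reference status is set when its two PCR results differ;
- first-half against second-half central results are reported separately as a check on drift;
- the contrast is described as POC testing against batched, transferred central testing.

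If double testing of later samples is not intended, section 9.2.2.1 must be corrected instead, and the comparison acknowledged as confounded with period.

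The cost is a change of analysis wording, plus separate data fields for the POC and central results. No extra samples or tests are needed, since section 9.2.2.1 already provides for both.

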5.2 Secondary Outcome Measures

Secondary outcome measures of the study are based on:

- (i) Economic measures, including resource use associated with the multiplex PCR testing and conventional blood culture
- (ii) The time to result for both the PCR test and its paired blood culture.

